### Patient Enrolment Criteria:

• Cataract in one or both eyes felt to be visually significant in the opinion of the patient and operating ophthalmologist.

### Patient Exclusion Criteria:

- Fellow eye has an irreversible cause of visual impairment
- Any prior ophthalmic surgery in the proposed operative eye
- Any co-morbid condition in the operative eye likely to impact post-operative visual acuity negatively (conditions only detected on post-operative examination would also lead to retrospective exclusion)

Intervention: Standard surgical training (as described below for "Control") plus a new, bespoke simulation-based training scheme using low cost, reusable model eyes combined with practical surgical exercises, developed in Africa by ICEH collaborator [name]. *See page 17*.

**Control**: Standard surgical training (without the bespoke training scheme that uses simulation and model eyes) in the ORBIS-COS administrated STEER project, mentioned above. Trainees complete 2-4 weeks of didactic lectures, surgical observation, and wet-lab training at a provincial training centre with a minimum of 50 pig eye wet-lab simulations per trainee. After observed mastery of wet-lab pig eyes, trainees then perform hands-on training in County level hospitals. The hands-on training pairs a surgeon from the training centre who travels to the county level hospital to mentor the trainee through a minimum of 30 assisted surgeries, and 50 'independent' surgeries under supervision. This project and its cataract surgical training protocol have been approved by the Chinese National Blindness Prevention Committee, who are essential partners.

### Outcomes

Main outcome: Mean video grade of the first 10 successive supervised or assisted SICS cases (with patient consent) for each surgeon, using ICO-OSCAR. Two approaches to determine mean video grade will be employed to account for the variation in the number of surgical steps performed by trainees. Variation either arises from individual competence, with the assumption that more competent surgeons are given a larger role during surgery, or from the teaching style of different mentors, with an emphasis on conservative training.

Both approaches are equally significant for determining the main outcome, and differ solely in the number of steps graded.

- Mean video grade across all surgical steps of the first 10 successive supervised or assisted SICS cases (with patient consent) for each trainee surgeon, using ICO-OSCAR. This approach penalizes surgeons for executing less steps, assigning a score of 0 for steps not performed.
- Mean video grade across all trainee-completed steps of the first 10 successive supervised or assisted SICS cases (with patient consent) for each trainee surgeon, using ICO-OSCAR. This approach scores surgeons only on surgical steps they performed in consideration of the variation in mentors' teaching styles.

The graders are masked to surgeon/patient identity, using a file-sharing platform to transfer videos to graders and collate grading information. These 10 cases will be the first 10 out of 30 cases completed under the supervision of the STEER traine.

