#### Randomisation (stratified blocked randomization):

Participants who have reached the appropriate inclusion and exclusion criteria for the trial will be eligible for randomisation to 'intervention' or 'control'.

Eligible trainees completing baseline data collection will be enrolled into the study and stratified into 10 groups\* according to their training center and hospitals (home facilities). The hospitals with only one participant are combined to form a mixed group. Participants in each of the 10 stratified groups will be assigned at random to one of the study arms as shown in the following figure.

An independent statistician having no contact with participants will generate the randomization sequences (lists) using a computer system that is inaccessible until after recruitment. The random sequence includes three types: (1) A list of the mixed hospitals with only one participant; (2) A number of lists of the hospital with paired participants (3) Individual list(s) of the hospitals with more than two participants. Each random sequence comprises of sequence numbers and their corresponding codes (e.g. two letters plus a 4-digit number). Codes are used to represent the Intervention or Control group; a codebook is created for decoding the group allocations.

To preserve allocation concealment, a two-step procedure will be used for random allocation in each training center.

**Step 1**: Project manager (PM) sends randomization sequences to the Quality Control officer (QCO). QCO assigns a code to each participant from the randomization sequences. QCO update the random lists with participant's names and send it to PM. At the end of this step, neither the QCO or participants know what group the codes refer to.

**Step 2:** As soon as receiving result file from QCO, PM checks the codebook, update the file with participant's names and send it back to QCO. QCO allocates the participants into control and intervention groups and completes the random allocation.

The participants will know their group assignment. However, the staff(s) grading video recordings of assessments will be masked by having a randomized number assigned to each video.

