### The Intervention

All participants in both intervention and control groups will undertake the 2-4 week Orbis-COS STEER training course. This course will consist of didactic training, observation as well as a minimum of:

- 1) wet lab training with 50 pig eyes
- 2) assisting 30 surgeries, finishing one of more steps of the procedure, and
- 3) 50 independent operations under supervision.

Participants in the intervention group will be introduced to a variety of simulation-based surgical training techniques over 2 to 4 weeks. This additional training will involve a total of approximately 16 hours of video-based presentations, practical SICS procedures on model eyes, trainee feedback, and self-assessment of surgical performance using the simulation-OSSCAR scoring system. Specifically, this will involve breaking down the SICS cataract surgery procedure into stages. At each stage surgeons will be presented background knowledge and then practice that stage repeatedly using simulation. This sustained deliberate practice will be an enhancement to the STEER course, and not as a replacement of any part of the educational content. Within the first week of the course, 'intervention' arm participants will be introduced to the artificial eyes, practice the cataract surgery procedure using the Simulation-OSSCAR as a learning tool, and be provided with ongoing feedback. (See also Standard Operating Procedures (SOP) 9 through 19 for Model Eye Training).

It is excepted that surgeons will independently complete 8 SICS procedures by the end of the training period. The first two simulation SICS procedures on model eyes will be performed under supervision of the consultant trainer. The fourth and eighth SICS procedure will be recorded, uploaded to Cybersight, and assessed by PI [name] who will provide feedback to the trainee.

During this time, trainees in the control group are at liberty to spend time as they please.

Week	Knowledge & Understanding		SI [Practical skills lea wet-lab	kills arning & practice in / drv-labl	Attitudes & Assessment [Online, video-recording, and reflective learning]	
	Aim	Time / [Outcome]	Aim	Time / [Outcome]	Aim	Time / [Outcome]
1	Learning theory & expertise	20 minutes			Reflective learning	20 minutes
	Scleral tunnelling	20 minutes	Scleral tunnel	2 hours [perform 40 tunnels on apples]		
	Capsulotomy.	20 minutes	Capsulotomy	2 hours [perform 20 capulotomies on tomatoes, and 10 using Kitaro kit)		

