### **Prevention of Bias**

It is accepted that there will be variability in individual participants' inherent or natural surgical aptitude. In order to attempt to reduce the effects of this, the two groups will be balanced with regard to the baseline OSCAR scores of participants, and their total number of previous surgical cases. This however will only occur in final analysis, and not before randomisation or training.

All efforts will be made to standardise the training offered to the 'Intervention' participants. The intense simulation course will be held in the same Training Centres. The training will be conducted by experienced trainers who have undertaken a specifically designed 'Training the Trainers' course. All recordings of surgical procedures will be performed using the same recording system.

Video recordings of procedures will be allocated a random 7-digit number, and subsequently stored onto an encrypted computer, and a separate encrypted hard drive. This random number will be the only identifiable information available when the simulation/surgical procedure is assessed, thus masking the assessor to the participant's randomised group.

It is recognised that surgical education is complex and multi-faceted. However, every effort will be made to reduce 'contamination' bias. Participants will sign an informed consent form detailing that they will in no way share any of the details of the course or educational intervention with any surgeon who is not known to be in the same randomised group as themselves; for a minimum of six months following the end of the training programme in Tongren.

The PIs and co-investigators declare that they have no financial or other conflicts of interest that are relevant to this randomised trial.

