# Appendix 3a. ICO SICS OSCAR

		ICO-Ophthalmolog	y Surgical Competency Asse	ssment Rubric-SICS (ICO-OS	SCAR: SICS)	
Oute		Navice (score = 2)	Beginner (score = 3)	Advanced Beginner (score = 4)	Competent (score = 5)	Not done. Done by preceptor (score= 0)
1	Draping	Unable to start draping without help.	Drapes with minimal verbal instruction. Incomplete lash coverage.	Lashes mostly covered, drape at most minimally obstructing view.	Lashes completely covered and clear of incision site, drape not obstructing view.	
2	Scieral access & Cauterization	Unable to successfully access sciena. Casterization insufficient or excessive both in intensity and localization.	Accesses sclera but with difficulty and hesitation. Cauterization insufficient or excessive in location or intensity.	Achieves good scleral access with mild difficulty. Adequate casterization.	Precisely and defily accesses sclera. Appropriate and precise cauterization.	
3	Scierocorneal Tunnel	Inappropriate incision depth, location, and size, hesitant dissection. Iris prolapse may occur	One of the following correct: incision depth, location or size. Able to dissect forward but not able to perceive depth	Two of the following are correct: incision depth, location or size. Understands that tunnel depth is incorrect but unable to correct.	Good incision depth, location and size. Tunnel constructed at right plane, if inappropriate plane, able to rectify.	
4	Corneal entry	Hesitant kenatome entry into AC. Unable to extend the internal valve. Significant shallowing of anterior chamber. Require wound extension or suturing.	Enters into AC but difficulty in extension. Follows a different plane. Entry either anterior or posterior to dissection site. Mild AC shallowing. Require wound extension or suburing.	Entry at right plane. Able to extend but with repeated use of viscoelastic. Internal valve irregular. Require wound extension or sataring.	Fluently enters in right plane. Wound length adequate with no further need for extension. Retains viscoeflastic during extension. Self-sealing, provides good access for surgical transecvering.	

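### The all-steps co-primary scores 0 for every step the mentor keeps, and no stated rule masks the mentor to arm, so masked video grading cannot guard it against arm-dependent hand-over

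*Combined protocol and SAP*

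**What the plan says.** The Outcomes section of the combined protocol and SAP defines two co-primary means over each surgeon's first ten supervised or assisted cases and gives them equal standing. The first covers all steps: "This approach penalizes surgeons for executing less steps, assigning a score of 0 for steps not performed". The second covers only the steps the trainee completed. The section explains that the number of steps varies with competence, "with the assumption that more competent surgeons are given a larger role during surgery, or from the teaching style of different mentors".

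In Appendix 3a the zero column of the rubric is headed "Not done. Done by preceptor (score= 0", and the performed grades run from 2 (Novice) to 5 (Competent).

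On the graded cases, Outcomes says "These 10 cases will be the first 10 out of 30 cases completed under the supervision". The Intervention section sets a low minimum role for the trainee in the assisted operations: "assisting 30 surgeries, finishing one of more steps of the procedure".

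On who knows what:
- Randomisation section: "The participants will know their group assignment". Video graders are masked by a random number on each video.
- Informed Consent: the person seeking patient consent should not know the surgeon's group.
- Control paragraph (printed under Patient Exclusion Criteria): the programme "pairs a surgeon from the training centre who travels to the county level hospital to mentor the trainee".
- Prevention of Bias: "The intense simulation course will be held in the same Training Centres". Trainees also pledge not to share course details with surgeons outside their own group for at least six months.

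The available text contains no rule that masks the mentor. The Statistical Analysis section specifies GEEs, with and without adjustment for baseline surgeon and patient factors. It names no centre, hospital or mentor term.

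**The concern.** Grader masking protects the grade of a step the trainee performed. It cannot protect the earlier decision, made in theatre, about whether the trainee performs the step at all. In the all-steps score that decision moves an item from 0 to at least 2, however well or badly the step is then done.

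The decision lies at least partly with the mentor. That is my inference from the wording on the role trainees are given and from the rubric's preceptor label. The plan does not say it outright. A mentor who knows that a trainee had extra simulation practice could hand over more steps on that ground alone. The all-steps mean would then favour the intervention with no difference in skill. The planning difference of 1.0 point is itself defined across all steps, so the exposed measure is the one on which the trial was sized.

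**Working it through.** **Inputs.** From Sample Size Calculations: 14 surgeons per arm, 10 cases each, SD 1.0, ICC 0.57, difference 1.0, power 0.9, alpha 0.05 (sidedness not stated; I take it as two-sided), and 19 rubric categories scored 0 to 5. From Appendix 3a: 0 for a step done by the preceptor, 2 to 5 for a performed step. Assumed, because the documents give no figure: the number of extra steps per case handed over in one arm, k, and the grade those steps earn, g.

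**1. The plan's own figure.**
- Variance of a surgeon's ten-case mean: 0.57 + 0.43/10 = 0.613, so the SD is 0.783.
- SE of the difference between arms: sqrt(2 × 0.613/14) = 0.296.
- Noncentral t power with 26 df at a difference of 1.0: 0.902, which matches the stated 0.9.
- With 15% attrition, 14/0.85 = 16.5, so 17 per arm and 34 in total, as stated.

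**2. Shift caused by hand-over alone.** At equal skill, k extra steps at grade g move the 19-item mean by k × g/19. One step adds 2/19 = 0.105 at Novice, 3/19 = 0.158 at Beginner, and at most 5/19 = 0.263.

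**3. Chance of a significant result with no skill difference** (noncentral t, 26 df, SE 0.296, nominal 5%):

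| Extra steps per case | Grade | Shift | P(significant) |
|---|---|---|---|
| 1 | 2 | 0.105 | 6% |
| 1 | 3 | 0.158 | 8% |
| 3 | 2 | 0.316 | 18% |
| 3 | 3 | 0.474 | 34% |
| 5 | 3 | 0.789 | 73% |

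**4. Scale.** The full 1.0-point difference at grade 3 would need 19/3 = 6.3 extra steps per case. Six of the 19 items are global indices (wound neutrality, centration, tissue handling, spatial awareness, iris protection, speed). That leaves 13 procedural steps, so 6.3 is about half the operation in every case. Small distortions are plausible; one that produced the entire planning effect would be extreme.

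**5. What the second co-primary would show.** Suppose extra steps are handed over at equal skill. If they earn the trainee's average grade, the completed-steps mean does not move. If they earn less, it falls. In both cases the all-steps mean rises. Arm-dependent hand-over would therefore tend to appear as disagreement between the two outcomes. The plan has no rule for reading such disagreement. The completed-steps mean also still depends on which steps, easy or hard, are handed over.

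**The case against.** The plan saw mentor variation coming. It added the completed-steps score for that reason and ranked it equally with the all-steps score. This is the strongest point on the other side, and much of it stands: the two outcomes together are partly diagnostic. It does not repair the all-steps outcome, which can still be reported as significant by itself.

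The non-disclosure pledge in Prevention of Bias could, read literally, extend to a mentor who belongs to neither group. However, it is written against contamination, covers course details rather than allocation, and does not stop a mentor learning the arm by another route.

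Stratified randomisation by training centre and hospital helps to balance a mentor's general style. It cannot balance behaviour that differs by arm within one mentor, and neither can a centre or mentor main effect in the model. The absence of such a term is therefore not the cause of this problem.

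A larger role may be a real training effect, since the plan assumes that abler trainees are given more to do. That stands: the all-steps score cannot separate skill from expectation.

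A reader might infer that mentors do know the arm and favour the intervention group, or that the staff who teach the model-eye course also mentor the outcome cases. The documents show neither. They leave both possible, and the operating procedures cited for the model-eye training were not available to check. A reader might also take 34% or 73% as the trial's expected error rate. Those figures hold only if the assumed step counts occur.

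**Conclusion.** The concern holds as a risk of bias in the all-steps co-primary. Each step kept by the mentor scores 0, trainees are unmasked, mentors come from the centres that host the intervention, and no rule in the available text masks them. Grader masking does not reach this route. The size depends on an unknown: false-positive rates run from 6 to 8% for one extra step per case to 18 to 34% for three at grade 2 to 3, and 73% for five at grade 3. These assume equal skill, 14 surgeons per arm, the plan's SD and ICC, a two-sided 5% test and a 19-item mean. The completed-steps co-primary limits the damage but does not remove it, because the two outcomes rank equally and discordant results have no stated interpretation.

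**What to change.** In Prevention of Bias:
- State that mentors of the ten outcome cases are not told the allocation.
- Extend the existing pledge so that trainees do not disclose their arm to the mentor.
- Record mentor ID for each case, and the mentor's guess of arm once per trainee.
- Where the existing rota allows, avoid having model-eye course staff mentor the same trainee's outcome cases. This should not be a firm requirement, because the operations belong to a separately approved service programme.

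In Statistical Analysis:
- Report the number of steps performed, by arm, beside both co-primaries. The rubric's preceptor column already holds this information.
- State that an all-steps difference without a completed-steps difference will not be read as evidence of greater skill.
- Separately, include the training-centre/hospital randomisation stratum in the GEE, for precision and for standard errors that reflect the stratified design. This does not remove arm-dependent hand-over.

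The cost is protocol wording and a short log. Masking of mentors will be imperfect, and the guess of arm will show how imperfect. No change is proposed to how mentors supervise or take over.

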#### Secondary outcomes:

- Mean presenting logMAR visual acuity on post-operative day (POD) 1 of ten successive cases with patient consent per surgeon (measured using the BOOST [Better Operative Outcome Software Tool] application.
- Mean improvement in lines of visual acuity in operative eye at POD 1.
- Cost per trainee in each group.

### **Informed Consent**

Potential participant trainees will be informed of the training opportunity and this research study. Heads of Training Centres will be involved in the process and are co-investigators in the trial.

Surgeon participants will be informed in detail about the nature of the education-intervention study; all surgeons participating will be free to leave the study at any time. See Appendix 1a and 1b for detailed Information and Consent Forms. Surgeons who decline to take part in the study will be offered the standard STEER surgical training package without the bespoke training scheme that uses simulation and model eyes. Each participant eye surgeon attending the 2 to 4-week training and involved in this educational-intervention research will be invited to read and sign a consent form (Appendix 1).

Patient participants will be informed that the outcomes of their surgery will be recorded as per normal good clinical practice and standard care. Informed consent to video record their surgery will be obtained. A standard consent form (Appendix 4), similar to local consent forms that indicates permission to use standard clinical photography will be used. This form will indicate that, as part of an educational randomised control trial, some surgeons received additional training. This form will be read to patients in Chinese, if they are unable to read it; and they will be invited to sign. The individual seeking consent should not know which randomisation group the surgeon is in.

### Participant Withdrawal

Surgeon participants, in either the 'intervention' or 'control' group, are free to leave the study at any time. If this is the case for any participant, no effort will be made to recover any costs incurred or equipment provided. Data collected up to the point of withdrawal of consent will have been anonymised and securely stored, and will still be held and included in data analysis.

### Randomisation

#### Pre-randomisation baseline assessment

Following consent, participant surgeons will be evaluated. This will include evaluation of previous surgical experience, and introduction to the ICO OSCAR. They will then be assessed

using the baseline Simulation-OSSCAR (see Appendices 3a and 3b). This will involve three simulation procedures (these will be recorded, anonymised, and remotely assessed using the Simulation-OSSCAR). This provides the baseline score for all participants: intervention and control.

#### Randomisation (stratified blocked randomization):

Participants who have reached the appropriate inclusion and exclusion criteria for the trial will be eligible for randomisation to 'intervention' or 'control'.

Eligible trainees completing baseline data collection will be enrolled into the study and stratified into 10 groups\* according to their training center and hospitals (home facilities). The hospitals with only one participant are combined to form a mixed group. Participants in each of the 10 stratified groups will be assigned at random to one of the study arms as shown in the following figure.

An independent statistician having no contact with participants will generate the randomization sequences (lists) using a computer system that is inaccessible until after recruitment. The random sequence includes three types: (1) A list of the mixed hospitals with only one participant; (2) A number of lists of the hospital with paired participants (3) Individual list(s) of the hospitals with more than two participants. Each random sequence comprises of sequence numbers and their corresponding codes (e.g. two letters plus a 4-digit number). Codes are used to represent the Intervention or Control group; a codebook is created for decoding the group allocations.

To preserve allocation concealment, a two-step procedure will be used for random allocation in each training center.

**Step 1**: Project manager (PM) sends randomization sequences to the Quality Control officer (QCO). QCO assigns a code to each participant from the randomization sequences. QCO update the random lists with participant's names and send it to PM. At the end of this step, neither the QCO or participants know what group the codes refer to.

**Step 2:** As soon as receiving result file from QCO, PM checks the codebook, update the file with participant's names and send it back to QCO. QCO allocates the participants into control and intervention groups and completes the random allocation.

The participants will know their group assignment. However, the staff(s) grading video recordings of assessments will be masked by having a randomized number assigned to each video.

